##### **Part C – Delayed Recognition**

*Examiner: “Now I’m going to read a longer list of words to you. Some of them are words from the original list, and some are not. After I read each word, I’d like you to say “Yes” if it was on the original list or “No” if it was not. Was [word] on the list?”*

Read the words from the top of the columns down.

Check either the “Y” (Yes) or “N” (No) box next to each word to indicate the patient’s response.

Guessing is allowed.

If the test is discontinued or omitted, please mark this on the bottom of the test form and indicate the reason.

The score for this portion of the HVLTR is the number of list words (i.e. words that in CAPS) correctly identified (“yes” response) minus the number of non-list words (i.e. words in lower case) incorrectly identified (“yes”

response). Therefore, the actual score can range from –12 (no list words identified and all non-list words identified) to +12 (all list words identified and no non-list words identified).

## **END NEUROCOGNITIVE TEST BATTERY**

**You have now completed the neurocognitive test battery.**

### **Summary of Requirements for Examiner Approval for the EORTC 1709 study**

Prior to testing a patient, potential examiners must:

Read “Certification & Administration procedures for the Neurocognitive Test Battery and PRO Questionnaires”

Contact [name] ([[contact]](mailto:[contact])) to obtain website and password information to get access to a password-protected website with all the necessary information

Obtain instructions and copies of the neurocognitive tests from the password-protected website in Dutch, English, French, German or Italian

Watch the training video available at the password-protected website

Complete the training video post test available at the password-protected website

Complete a “practice” assessment (see 1.1)

Complete the Certification Worksheet (see Appendix K)

Send ALL completed documents (training video post test, test forms of “practice” assessment and signed Certification Worksheet) to the attention of [name].

Scan documents and EMAIL: [[contact]](mailto:[contact])

### **Summary of Testing Patients for the EORTC 1709 study**

Certified examiners must:

Inform the patient of the date for neurocognitive assessment.

On date of testing, neurocognitive testing should be completed in one session:

Test instructions (see 1.3) must be followed verbatim with every patient at every study visit.

All tests should be completed in black pen.

All test results are recorded on the test forms.

In the event that a patient cannot complete a test, specify the reason(s) on the test form.

All test forms must be signed clearly by test administrator with correct study identifiers.

Before dismissing the patient, thank the patient for cooperation.

Remind of next appointment and that these tests will be repeated.

Patients should not be given copies of their tests to avoid learning the material between test administrations.

Please keep original test forms at site. In the event of questions, contact [name].

Send ALL completed documents (neurocognitive scoring forms) as soon as possible to the attention of [name].

Scan documents and EMAIL: [[contact]](mailto:[contact])

# Appendix L: Specific protocol instructions during the COVID-19 pandemic

Note: All instructions listed in this Appendix will be solely applicable during the COVID-19 crisis. Furthermore, please ensure that any protocol deviations resulting from COVID-19 are:

- Adequately documented in the eCRFs as well as the patient's medical records or in a NTF to be stored in your Study binder (ISF).
- Always begin deviation text with "COVID-19"

## Introduction

Current information suggests that cancer patients have a higher risk of infection and serious complications from infections including COVID-19, than other patients.

It is strongly recommended that investigators exercise medical/clinical judgement, and decisions regarding each patient should be individualized after considering the overall goals of treatment, the patient's current oncologic status and treatment tolerance as well as their general medical condition.

In addition, investigators should adhere to local and institutional guidelines for SARS-CoV-2 infection and suspected COVID-19 infection.

## Risk-benefit assessment

### Introduction to trial

The EORTC trial 1709 is a randomized phase III trial in which the standard of care for patients with newly diagnosed glioblastoma, consisting of temozolomide-based chemoradiotherapy, is compared with the same treatment combined with marizomib, a novel proteasome inhibitor. Its purpose is to compare safety and efficacy of the experimental therapy with the current standard of care.

### Benefits

In September 2020, the IDMC committee did recommend stopping the study's recruitment by lack of evidence regarding the survival benefit (Refer to Section 1.2.1)

### Risks related to the trial especially during the COVID-19 crisis

There are potential risks associated with the treatment administered in the trial, and during the COVID-19 crisis, these risks may be increased:

- The fact that included patients need to come for regular visits to the hospital, increases their exposure risk to persons who are contagious for SARS-CoV-2. General rules like social distancing (1.5 m) and avoidance of persons with possible signs or confirmed diagnosis can be applied. However, SARS-CoV-2 can also be contagious in persons who do not have symptoms, so every hospital visit increases the risk of attracting SARS-CoV-2 infection.
- The treatment regimes in both arms may impair the patients' immune system. This may lead to an increased risk of acquiring a SARS-CoV-2 infection with subsequent occurrence of COVID-19 including complications up to death.
- Deviations on the treatment regimen, e.g. delays and interruptions, related to the COVID-19 crisis, can negatively influence the efficacy of the drugs and thus the benefit for the patients on trial

### COVID-19 vaccination:

As per the European Medicines Agency (EMA):

If physicians decide to administer SARS-CoV-2 vaccines in patients enrolled in the study, decisions should be individualised based on the risk of SARS-CoV-2 complications and potential benefit from the vaccine, general condition of the patient and the severity of COVID-19 outbreak in a given area or region and in accordance with the vaccine label. Furthermore, the Country guidelines and/or institutional guidelines must be followed.

Treatment schedule should not be altered because of the COVID-19 vaccination.

The administration of a SARS-CoV-2 vaccine stating the name of the vaccine used (e.g. Moderna, Pfizer BioNTech, AstraZeneca Oxford, ...) shall be added in the concomitant medication form in the eCRF and noted in the patient's medical file. Any possible vaccine related AE should be captured in the AE forms in the eCRFs, specifying the potential relationship to the vaccine.

### **Proposed measures for patients already enrolled during the COVID-19 crisis and recruitment**

The study coordinators in collaboration with EORTC, propose the following guidelines as long as the current COVID-19 crisis is ongoing.

Please ensure that any protocol deviations resulting from COVID-19 are:

Adequately documented in the eCRFs as well as the patient's medical records or in a Note to file (NTF) to be stored in your Study binder (ISF)

Always specify the reason of the deviation: "COVID-19"

All COVID-19 related deviations have to be reported to EORTC HQ via [[contact]](mailto:[contact])

## **1. Recruitment of new patients**

The trial is closed to recruitment.

## **2. Guidelines for study assessments**

### **2.1 With respect to study imaging procedures:**

For the baseline study imaging procedures, the protocol requirements have to be fully met.

For on-study imaging procedures, it is preferred that the patient have imaging performed at the investigative site as directed in the protocol.

If difficulties are encountered to perform the imaging as per the protocol, there are several possibilities, in order of preference:

Have the imaging performed offsite, locally according to the protocol-specified timing. Guidance should be given by the site to the local imaging facility about conducting scans according to all applicable requirements (modality etc. as per 1709 Imaging Guidelines).

Have the imaging performed at the site but delayed to a significant extend (a window of 2 weeks instead of 1 week will be allowed) due to travel restriction/safety of the participant.

Have the imaging performed offsite but delayed (a window of 2 weeks instead of 1 week will be allowed) due to travel restriction/safety of the participant.

Skip the imaging only if impossible to perform due to travel restriction/safety.

**For all above situations, site needs to report this in the comment fields of the applicable CRFs as well as in the Source Data.**

## **2.2 With respect to study treatments:**

In general, patients with a deadly cancer such as glioblastoma should receive the best possible treatment, also during the ongoing pandemic. Withholding or interrupting tumour-specific treatment should therefore be avoided whenever possible. For the ongoing EORTC-1709 (MIRAGE) trial, the goal is therefore – taking in account directives of local and national authorities - to treat patients as closely to the protocol guidelines as possible, without endangering their safety and keeping the risk/benefit ratio for the patient acceptable.

Patients on treatment will be treated as per protocol, in both arms. Protocol assessments should be performed as per protocol as much as possible. Again, taking in account local and/or national directives.

Assessments should be done at the investigative site if possible.

In the event it is not possible or not in the best interest of a patient to travel to the treating site because of COVID-19, the following options are proposed (depending whether IMP administration is required during the visit):

If assessments are required prior to study treatment administration, as stated in the protocol (chapter 6, “Clinical evaluation, laboratory tests and follow-up”) and administration of study treatment cannot be postponed the following should be considered:

Arrange the exact date of the visit (and time) in the centre and perform the assessments in advance

Provide standard laboratory assessments (as described for the respective visit in chapter 6 “Clinical evaluation, laboratory tests and follow-up”) of the subject either by qualified staff of contracted laboratories or contractually secured healthcare providers whom employ appropriate safety measures and excludes patients whom are quarantined or living with or have been quarantined with a confirmed COVID-19 case

Treatment related laboratory exams can be done in certified offsite facilities.

Visits that do not involve administration of study treatment, and that cannot be met because of the COVID-19 crisis, can be replaced by a telephone consultation.

These deviations will not to be considered as protocol violations and must be documented clearly both in the eCRFs as well as in the patients' medical file on site as a COVID-19-related deviation (please specify every deviation in the eCRF with “COVID-19”). All other COVID-19-related deviations to the protocol will be documented equally. In case of doubt, the 1709 medical monitor can always be contacted to discuss ([[contact]](mailto:[contact])). COVID-19-related deviations will not be considered protocol violations as long as they do not endanger the safety of the patient.

With respect to Marizomib (MRZ):

It is advised to follow protocol treatment as closely as possible under the present circumstances for both treatment arms, in the best interest of the patient. Skipping or interrupting treatment will also follow the protocol guidelines, the same as for toxicities or non-toxicities (see chapter 5 of the protocol “Therapeutic regimens, expected toxicity, dose modifications”). Interruptions exceeding the described period (e.g., 3 consecutive marizomib administrations or a full cycle in both arms) must be discussed with the medical monitor

([[contact]](mailto:[contact])) to decide if it is still in the best interest of the patient to restart the treatment or further delay.

Marizomib (MRZ), seen the parenteral administration (IV) and the tight timelines between start of reconstitution and start of administration, must be administered at your institution. Delays and skipping of administration are allowed as described in the protocol (chapter 5 “Therapeutic regimens, expected toxicity, dose modifications”).

### **With respect to Temozolomide (TMZ)**

TMZ will continue to be distributed to the patient as per the sites local practice.

#### **2.3 With respect to patient physical visits:**

Patient physical visits which do not require study treatment administration or are not crucial for the safety of the patient can be changed in phone visits where needed.

#### **2.4 With respect to patient reported data:**

Quality of Life (QoL) questionnaires can be collected through phone or a video conference. Voice scripts are available on the study web documentation.

If phone assessment cannot be arranged, the QoL questionnaires can be collected by providing the questionnaires to the patients. Patients should be instructed to complete the questionnaires within the intended timepoint (according to protocol). Patients should also complete the date on the form with the date they completed the questionnaire. Sites are requested to make their own guidelines to patients in their own language.

MMSE and neurocognitive testings cannot be collected through phone or video conference. If impossible to perform due to travel restriction/safety, a protocol deviation should be documented as this is not according to protocol.

#### **2.5 With respect to collection of biomaterial:**

If the collection of a sample is part of the inclusion criteria (FFPE tumor tissue block or 24 unstained slides) and if impossible to collect the sample(s) due to travel restriction and/or safety concerns, the patient cannot be enrolled in the trial.

The collection of sample(s) can be skipped only if all following (2) criteria are met

- The HBM samples are not part of the inclusion criteria and
- The collection of the HBM samples is impossible to perform due to travel restrictions and/or safety concerns.

If these 2 criteria are fulfilled, the sample collection can be skipped and a deviation must be entered, as this was not according to the protocol.

#### **2.6 With respect to collection of RTQA**

Concerning the mandatory central review of the treatment plan for the first two patients per site, we acknowledge that timely submission of the data by investigators and review by our reviewers may not be feasible during this pandemic with reduced personnel. We ask that you continue to send the data for all patients (those for prospective or retrospective review) as soon as possible and we will continue to send the cases to our reviewers asking also for their evaluation as soon as possible. Despite this, as a temporary measure, please do not hold up a patient’s treatment waiting for review and proceed as planned. We will inform you when processes should be returned to timely reviewing.

#### **2.7 With respect to on-site monitoring visits**

All on-site monitoring visits are currently suspended. CRAs will contact your staff to schedule the next monitoring visit, when the situation will evolve positively and in compliance with the Governments and sites recommendations. In the meantime, EORTC 1709 study team will keep in touch with your staff to provide any support deemed necessary.

### 3. Serious adverse event reporting:

- Sites should follow the SAE reporting as described in the protocol e.g. the sites should continue to report SAEs immediately and no later than 24 hours from the time the investigator or site staff became aware of the event, as described in the protocol. There are no specific adaptations to the protocol defined SAE reporting procedure due to COVID-19.
- Should sites have any SAE reporting related questions, please contact us at [[contact]](mailto:[contact])
- Should there be a suspected or confirmed serious case of COVID-19 infection, report it as SAE:
  - Please remember to provide the mandatory SAE information as per protocol and as per the CRF completion guidelines.
  - Please indicate if the COVID-19 infection was confirmed by a test.
  - Please provide as much information as available.

### 4. Informed consent

In all participating countries, except Germany, if an amendment is currently ongoing requiring re-consent of already enrolled patients and/or additional consent is necessary for the implementation of new urgent changes in trial conduct (mainly expected for reasons related to COVID-19), alternative ways of obtaining such re-consents should be considered during the pandemic e.g. contacting the trial participants via phone or video-calls and obtaining oral consents supplemented with email confirmation. Any consent obtained this way should be documented and confirmed by way of normal consent procedures at the earliest opportunity when the trial participants will be back at the regular sites.

PD	Progressive disease
PFS	Progression-free survival
PK	Pharmacokinetics
PO	Orally (per os)
PP	Per Protocol Population
PT	Preferred term

QLQ-BN20	Quality of Life Questionnaire Brain Cancer Module
QLQ-C30	Quality of Life Questionnaire C30
QoL	Quality of life
RANO	Response Assessment in Neuro-Oncology
RT	Radiotherapy
SAE	Serious adverse event
SAP	Statistical analysis plan
SE	Standard error
SGOT	Serum glutamic oxaloacetic transaminase (AST)
SGPT	Serum glutamic pyruvic transaminase (ALT)
SP	Safety population
SSC	Study Steering Committee
TMZ	Temozolomide
TR	Translational Research
TTE	Time to event
TTF	Tumor treating fields
uMGMT	Unmethylated MGMT
ULN	Upper limit of normal
US	United States
UV	Ultraviolet
WHO	World Health Organization

2. Introduction

The intergroup Study (EORTC-1709-BTG) protocol v7.0 which was issued on 22 OCT 2019 planned a review of study data by the Independent Data Monitoring Committee (IDMC) for futility and safety. The clinical cutoff date for this analysis was 28 APR 2020 when 88 deaths were initially observed as requested by study design. After data update and cleaning, the database was locked on 07 AUG 2020. The IDMC performed the study review on 14 SEP 2020. At the cutoff date, 616 patients were randomized and 106 deaths were reported. Although the trial results did not cross the pre-specified futility boundary, the IDMC observed that there was as yet no evidence that marizomib provides a benefit in survival. The statistical data presented also suggested that it was extremely unlikely that a difference would emerge with additional patients or further follow-up. The IDMC observed that marizomib in this combination induced severe neurological and neuropsychiatric disorders, as well as other treatment-related Grade 3-4 side effects, in a substantial proportion of the patients. The IDMC therefore recommended that the study be discontinued from further recruitment and that results be disclosed to the medical community as soon as possible. However, if patients still on treatment were tolerating marizomib, they were allowed to continue, if so wished by the patient and treating physician. The IDMC did not request that a further interim analysis be implemented.

Following the IDMC recommendation, the patient recruitment was prematurely closed. The total number of randomized patients was 749 (750 planned). The results of the study were prematurely disclosed to the study investigators and to Celgene, a BMS company, and Bristol Myers Squibb (BMS). An amended study protocol v8.0 was released on 30 SEP 2020 to reflect that the interim OS analysis performed is considered as the primary OS analysis of the study.

For the publication of the primary analysis results, a new database lock will be performed in mid 2021 at the same cut-off date (28 APR 2020) as for the IDMC review but with cleaner data for, primary endpoint, study treatment exposure, safety and other secondary endpoints.

All randomized patients will be followed till the total number of overall survival (OS) events for the initially planned final analysis is observed (488 deaths in the intent-to-treat [ITT] population and 320 in the unmethylated O-6-methylguanine-DNA methyltransferase [MGMT] subgroup). The cutoff date of the long term follow-up analysis is expected Q2 2022. The number of deaths will be closely monitored, ie, every three months. More frequent monitoring might be decided when number of deaths in the ITT population gets closer to 488. At that date, a long term follow-up analysis will be performed with more mature data for all endpoints. As the primary results will have been already released, the intent of this long term follow-up analysis is for descriptive purposes only.

The original signed statistical analysis plan (SAP) should be amended and signed to describe the analyses and data presentations for the current primary analysis and the long-term follow-up analysis.

The purpose of SAP v2.0 is to ensure the credibility of the study findings by pre-specifying the statistical approaches to the analysis of study data prior to database lock. The SAP was prepared by European Organisation for the Research and Treatment of Cancer (EORTC) and reviewed by BMS. It contains definitions of analysis populations, derived variables and statistical methods for the analysis of efficacy and safety. It describes analysis conventions to guide the statistical programming work. Throughout this SAP, the treatment arms are referred to as control and MRZ.

This SAP was finalized and signed prior to the clinical database lock for the primary analysis. All statistical analyses detailed in this SAP will be conducted using SAS[®] Version 9.4 or higher.

Compared to SAP v1.0 main changes in the SAP v2.0 are the following:

- Interim OS analysis becomes the primary OS analysis. The multiplicity strategy will be applied during this analysis.
- The long term follow-up analysis will be performed at 5% significance.
- The re-randomization test will not be performed because of lack of marizomib benefit following the review of the analysis of OS by the IDMC.

3. Use of the Statistical Analysis Plan

The primary analysis report will present the following sections of the SAP:

Section	Presented
7. Subject Disposition	All
8. Protocol Deviations/Violations	All
9. Demographics and Baseline Characteristics	All
10. Study Treatments and Extent of Exposure	All
11. Efficacy Analysis	All
12. Safety Analysis	All
13. Quality of Life Analysis	All

The long term follow-up analysis report will present the following sections of the SAP:

Section	Presented
7. Subject Disposition	All
8. Protocol Deviations/Violations	All
9. Demographics and Baseline Characteristics	All
10. Study Treatments and Extent of Exposure	All
11. Efficacy Analysis	All
12. Safety Analysis	All
13. Quality of Life Analysis	All

Important note: Further to the IDMC recommendations, marizomib will be discontinued per physician/patient decision with the consequence of a decreased exposure to marizomib compared to exposure planned in the protocol. All analyses will be performed in the populations planned in the protocol.

4. Study Objectives

To compare the overall survival of glioblastoma patients treated with standard temozolomide (TMZ)-based chemo radiotherapy alone or TMZ-based chemo radiotherapy in combination with marizomib.

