## 8.2.3 Statistical methods

### 8.2.3.1 Efficacy analyses

We will conduct all primary efficacy analyses in the intent-to-treat population.

In the primary analyses, differences between the treatment groups in OS will be assessed by a stratified LogRank test adjusted for the stratification factors assessed at randomization (except institution), testing the null hypothesis (H0):

- H0:  $HR_{MRZ\ arm/control} = 1$

Versus the alternative hypothesis (H1)

- H1:  $HR_{MRZ\ arm/control} < 1$

We consider this test as confirmatory and will perform it at a 1-sided significance level  $\alpha=0.015$  in the ITT population and  $\alpha=0.01$  in the uMGMT subgroup. If one of them is significant, the assigned alpha will be transferred to the other and the overall Type 1 error will be controlled at one-sided 2.5% by graphical method.

Kaplan-Meier survival curves (product-limit estimates) will be presented by treatment group, in the ITT population and by MGMT subgroup, together with a summary of associated statistics (median survival time, 6-, 12-, 18-, 24-month OS rate estimates and estimates for every 6 months thereafter as applicable) including the corresponding two-sided 95% confidence intervals (calculated by Greenwood formula's estimation of the standard deviation for rates and by Brookmeyer and Crowley technique for the median).

The hazard ratio (HR) (including two sided 97% and 95 % confidence interval in the ITT population and two sided 98% and 95 % confidence interval in the uMGMT subgroup) of the Marizomib group over the control group will be calculated by Cox's proportional hazards model stratified by the stratification factors assessed at randomization (except institution).

The primary analysis will take place after 488 deaths (320 uMGMT) deaths have occurred.

A re-randomization-test analysis will be performed to support the primary analysis in the ITT population and in uMGMT.

The re-randomization test will be performed as follows:

- The procedure will use 50,000 replications.
- Based on the value of their randomization stratification factors, for each replicate, subjects will be (virtually) re-assigned to treatments using the Medidata BALANCE minimization randomization algorithm in the order in which they were randomized into the trial.
- For each replicate the stratified log-rank test statistic adjusted by randomization stratification factors comparing the duration of overall survival will be computed.

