## 8.4 Follow-up analysis

Further to the recommendations of the IDMC, the patient recruitment had to be prematurely closed. The final number of randomized patients was 749 (750 planned). The results of this study had also to be prematurely disclosed. The interim analysis was considered as the final analysis of this study.

All randomized patients will be followed till the total number of OS events for the initially planned final analysis was observed (488 deaths). At that date, a follow-up analysis will be performed in accordance to the updated Statistical Analysis Plan for descriptive purpose only, with more mature data for all endpoints.

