4.1. Primary Objective

The primary objective of this study is to compare overall survival in subjects receiving marizomib (MRZ) in combination with control treatment (ie, TMZ with concomitant radiotherapy [RT], followed by TMZ maintenance therapy) (MRZ/TMZ/RT→MRZ/TMZ) with subjects receiving control treatment only (TMZ/RT→TMZ). The testing strategy is defined to assess this objective in both the ITT population and the uMGMT stratum with adequate statistical power.

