5.4. Sample Size Determination

For this study, we assumed that in the ITT population the standard treatment plus MRZ presents with a superior OS efficacy compared to the standard treatment alone, estimated by a hazard ratio (HR) equal to 0.74 (26% reduction of the hazard of death). This corresponds to a median OS of 16 months in the standard treatment alone compared to 21.6 months for standard treatment plus MRZ (Chinot OL, 2014) (Gilbert MR, 2014). We also assume that at the time of final analysis, the MGMT methylation status will be distributed to 60% unmethylated, 30% methylated and 10% undetermined. We also hypothesized that the MRZ effect would be mainly present in the uMGMT stratum where it would display a HR of 0.70 (median OS of 13 months in the control arm compared to 18.6 months for MRZ) (Chinot OL, 2014) (Gilbert MR, 2014). The effect in the mMGMT stratum would be $HR > 0.80$ and in the undetermined cases, which are assumed to be a balanced mixture of uMGMT and mMGMT cases, the effect would be in line with the overall population, ie, $HR = 0.74$.

Based on the network of the institution, it should be possible to recruit 400 subjects/year (150 subjects in the first year, and then 400 subjects per year).

For the primary endpoint of OS, the formal statistical testing is based on comparisons between two treatment groups in both ITT population and uMGMT stratum. We will use a graphical method to control overall Type 1 error at one-sided 2.5% (Bretz F, 2009). We have to recruit 750 subjects to show the OS difference with 86% power (taking into account the interim analysis for futility) and overall one-sided 1.5% significance in the ITT population and with 80.7% power and one sided 1% significance in the uMGMT stratum. We will recruit these subjects in about 30 months and will follow them up for about 19 months, the time necessary to observe the required 488 deaths

(320 in uMGMT) for the primary analysis. We will perform the test in the ITT population and in the uMGMT stratum simultaneously. If one of them is significant, we will attribute the assigned alpha to the other. At the final analysis, we will provide treatment effect estimates in the uMGMT stratum, in the mMGMT stratum and in the undefined MGMT stratum.

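### SAP 11.2 tests OS at one-sided 1.5% and 1% but omits the protocol's matching 97%/98% intervals and stratified uMGMT hazard ratio, and SAP 5.4 still gives the 488/320-death power to an analysis with about 106 deaths

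*SAP*

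**What the plan says.** **Which analysis is primary.** SAP section 2 makes the look with cutoff 28 April 2020 the primary OS analysis: "Interim OS analysis becomes the primary OS analysis. The multiplicity strategy will be applied during this analysis". It adds "At the cutoff date, 616 patients were randomized and 106 deaths were reported", and says that "a new database lock will be performed in mid 2021 at the same cut-off date (28 APR 2020) as for the IDMC review". SAP 11.2 runs the primary analysis on the deaths available at that new lock. It assigns 488 ITT and 320 uMGMT deaths to the long-term follow-up analysis, which SAP section 2 calls descriptive. Protocol 8.4 agrees: "The interim analysis was considered as the final analysis of this study".

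**Where the earlier meaning survives.** SAP 5.4 says 750 subjects are needed to "show the OS difference with 86% power (taking into account the interim analysis for futility) and overall one-sided 1.5% significance in the ITT population", gives 80.7% power at one-sided 1% for uMGMT, and describes the required deaths as 488, with "320 in uMGMT) for the primary analysis". SAP 4.1 says the strategy assesses OS in "both the ITT population and the uMGMT stratum with adequate statistical power". Protocol 8.2.3.1 still reads "The primary analysis will take place after 488 deaths (320 uMGMT) deaths have occurred".

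**Tests and estimates.** SAP 11.1 and 11.2 keep the 1.5%/1% split, with alpha passing from a rejected hypothesis to the other, for the redefined primary analysis. Protocol 8.2.3.1 pairs those tests with a stratified Cox hazard ratio, with two-sided 97% and 95% intervals in ITT and 98% and 95% in uMGMT. SAP 11.2 specifies a stratified Cox hazard ratio with a 95% interval in ITT. The only hazard-ratio model it names for uMGMT is the unstratified subgroup model. SAP 5.4 promises treatment effect estimates in uMGMT but names neither a model nor an interval.

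**The concern.** There are two separate matters.

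- **Interval and test do not correspond.** A one-sided 1.5% test goes with a two-sided 97% interval, and a one-sided 1% test with a 98% interval. A 95% interval can exclude 1 when the confirmatory test has not rejected. In uMGMT the confirmatory test is stratified while the only named model is not, so the estimate would not belong to the test beside it.
- **The stated power belongs to another dataset.** A reader who takes SAP 5.4 at its word would see a non-significant primary result as coming from a test with 86% power. The follow-up at 488/320 deaths, where that power applies, is no longer the confirmatory test.

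**Working it through.** **Inputs.** Hazard ratio 0.74 (ITT) and 0.70 (uMGMT), 488 and 320 deaths (SAP 5.4); 1:1 allocation (SAP 5.3); one-sided 1.5% and 1% (SAP 11.1); 106 deaths reported at the cutoff (SAP section 2); futility look at 88 deaths with boundary 1.12 (Protocol 8.3).

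**Formulas** (log-rank, normal approximation, D deaths):
- Power = Φ(½√D × |ln HR| − z)
- Critical HR = exp(−2z/√D)
- z = 2.170 (1.5%), 2.326 (1%), 1.960 (2.5%)

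**1. Reproducing the design.**
- ITT, 488 deaths: 11.045 × 0.3011 = 3.326; 3.326 − 2.170 = 1.156; power 87.6%. If the futility boundary is obeyed at 88 deaths (bivariate normal, correlation √(88/488)), power is 86.1%, against the stated 86%. The stopping probabilities are 29.8% under no effect and 2.6% at 0.74, as in Protocol 8.3.
- uMGMT, 320 deaths: 8.944 × 0.3567 = 3.190; 3.190 − 2.326 = 0.864; power 80.6%, against the stated 80.7%.

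The design figures are therefore right for 488 and 320 deaths.

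**2. ITT at the analysis now called primary.** With 106 deaths, 106/488 = 21.7% of the planned number:
- Power: 5.148 × 0.3011 = 1.550; 1.550 − 2.170 = −0.620; 26.8%.
- Critical HR: exp(−2.170/5.148) = 0.656, against 0.822 at 488 deaths.
- If the new lock changes the count: 25.3% at 100 deaths, 27.7% at 110, 30.1% at 120.

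**3. uMGMT.** The documents do not give uMGMT deaths at the cutoff. The design share, 320/488 = 65.6%, implies 69.5, say 70.
- At 70 deaths: 4.183 × 0.3567 = 1.492; 1.492 − 2.326 = −0.834; power 20.2%, critical HR 0.573 (0.771 at 320 deaths).
- Assuming 55% to 70% of 106, that is 58 to 74 deaths: about 17% to 21%. Allowing for alpha passed on from ITT (simulation, correlation √(uMGMT deaths/106)): about 22% to 27%.

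**4. Size of the interval mismatch, before alpha is passed on.**
- ITT, 106 deaths: the 95% interval excludes 1 below exp(−1.960/5.148) = 0.683, while the test needs 0.656 or lower. The gap is 0.656 to 0.683 (0.661 to 0.688 at 110 deaths).
- Example: HR 0.67, standard error 2/√106 = 0.194. The 95% interval is 0.458 to 0.980, the 97% interval 0.440 to 1.021, and one-sided p = 0.0196, which is above 0.015.
- uMGMT, 70 deaths: the gap is 0.573 to 0.626 (0.543 to 0.598 at 58 deaths; 0.582 to 0.634 at 74).

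**The case against.** The case for leaving the text alone has several parts.

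- **Disclosure.** SAP section 2 and 11.2 state openly the redesignation, the cutoff, the 106 deaths and when each analysis is run. SAP 5.4 is a carried-over sample-size section, and no analyst would run the primary analysis at the wrong time. This stands, and it reduces the SAP 5.4 and Protocol 8.2.3.1 defects to stale labels. But SAP 5.4 is not marked as history and uses the very term that SAP v2.0 redefined.
- **Power after the event.** The IDMC had already reviewed the data, and a planned interval shows precision directly. It is true that stating power now changes no decision. The request is only that the stated power not belong to a different analysis, and it uses the death count and design hazard ratios, not the observed effect.
- **The protocol still governs.** Nothing in the SAP revokes the 97%/98% intervals, and the opening of SAP section 11 promises two-sided intervals alongside the tests. But SAP 11.2 names 95% explicitly and SAP 6.1 makes it the default, so an analyst following the SAP would produce only that.
- **Passed-on alpha.** If one hypothesis is rejected, the other is tested at one-sided 2.5%, for which 95% is the matched interval. This is correct and limits the mismatch to the initial levels.

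Two stronger readings are tempting. A reader might infer that the change was made silently, because the list of main changes in SAP section 2 does not mention it. That list compares with SAP v1.0, which is not available, so its silence shows nothing. A reader might also infer that the uMGMT result is an open question. Protocol 8.3 lets the IDMC weigh a suggested uMGMT effect, and the documents record no such reservation. The re-randomization test was planned in ITT and uMGMT, and SAP 11.2 drops it because there was no significant result to validate. A significant uMGMT result is therefore remote, though not strictly excluded.

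**Conclusion.** The point holds as a reporting and labelling defect. Followed as written, the SAP would report a 95% interval beside a 1.5% test in ITT, and no stratified hazard ratio or 98% interval for the 1% test in uMGMT, although Protocol 8.2.3.1 requires both. SAP 5.4 attaches 86%/80.7% power to an analysis that has about 27% in ITT and, on assumed death counts, about 17% to 21% in uMGMT before alpha is passed on. The ITT figure rests on 106 deaths and moves only to 25% to 30% for 100 to 120. The uMGMT figure rests on an assumed 55% to 70% share of deaths.

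The low power should not be read as a fault in the IDMC recommendation, in the redesignation or in the use of the full alpha. Nor is the type I error inflated: in the same simulation under no effect, the chance of any rejection is about 2.0% to 2.1%, within 2.5%. The trial's conclusion is unlikely to change.

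**What to change.** - **SAP 11.2, primary analysis.** Restore the 97% (ITT) and 98% (uMGMT) intervals beside the 95% ones, and specify the stratified Cox hazard ratio in uMGMT as well as ITT. Add that if one hypothesis is rejected and its alpha passes on, the 95% interval is the matched one for the other.
- **SAP 5.4 and 4.1.** Label the 86%/80.7% power, the 488/320 deaths and the power claim in the objective as the original design. Say that 488/320 deaths now trigger the long-term follow-up analysis. State the power or critical hazard ratio of the redefined primary analysis at its actual ITT and uMGMT death counts, using the design hazard ratios (ITT at 106 deaths: about 27%, critical value about 0.66).
- **Protocol 8.2.3.1.** Align the trigger for the primary analysis with Protocol 8.4 and SAP 11.2.

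The cost is wording in both documents, one further Cox model and two further intervals. The stated power becomes less favourable. No new data, tests or follow-up are needed, and the primary test is unchanged.
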